4.3.2.1 Atezolizumab SC

Atezolizumab (1875 mg) SC injections will be administered subcutaneously by a health care professional in the anterior thigh region per the instructions outlined in Table 1.

The injection site should be alternated between the left and right thigh. New injections should be given at least 2.5 cm from the old site and never into areas where the skin is red, bruised, tender, or hard. In all cases, start and stop times of the SC injection should be captured.

No premedication will be allowed for the first dose of atezolizumab SC. Premedication may be administered for Cycles ≥ 2 at the discretion of the treating physician. Injection sites will be digitally photographed after a SC injection if a severe adverse reaction at the injection site is observed. Digital recordings will be stored at the site.

In case a participant develops unacceptable toxicity to the SC injection of atezolizumab, treatment with IV infusion may continue. In case a participant develops toxicity that is linked to the treatment with atezolizumab irrespective of the form of administration (SC or IV), further continuation of treatment is not recommended. Refer to Appendix 9 for further guidance on atezolizumab toxicity management.

Administration of atezolizumab SC will be performed in a monitored setting where there is immediate access to trained personnel and adequate equipment and medicine to manage potentially serious reactions. For anaphylaxis precautions, see Appendix 8. Atezolizumab SC injections will be administered per the instructions outlined in Table 1.

Table 1 Administration of First and Subsequent Atezolizumab SC Injections

First and Subsequent SC Injections

 • No premedication is permitted prior to the first SC injection. • For subsequent SC injections, if the participant experienced an injection-related reaction with any previous injection, premedication with antihistamines, antipyretics, and/or analgesics may be administered at the discretion of the investigator. • Vital signs should be measured as described in Section 4.5.4. • Participants should be informed about the possibility of delayed post-injection symptoms and instructed to contact their study physician if they develop such symptoms

PK=pharmacokinetic.

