4.5.8.2 Description of Clinical Outcome Assessment Instruments *Patient Preference Questionnaire*

The PPQ is a generic preference questionnaire designed to ask patients about which route of administration they preferred after receiving both the SC and IV formulations. Question 1 asks patients to report their preference for the route of administration (IV, SC, or no preference). Question 2 asks patients to rate the strength of their preference (if any) on a 3-point scale (very strong, fairly strong, not very strong). Question 3 asks patients to provide two main reasons for their preference (see [Appendix 4](#)).

The PPQ will be completed immediately after 3 cycles of each treatment (i.e., Day 1 of Cycle 6 of the Treatment Crossover Period) to allow participants to have experience with both routes of administration and to determine if additional treatment by one route or another modified their preference. Please refer to [Appendix 1](#) for instructions regarding when participants who prematurely discontinue study treatment should complete the PPQ.

Therapy Administration Satisfaction Questionnaires

Participant-reported treatment satisfaction with atezolizumab IV and atezolizumab SC will be evaluated using the TASQ-IV and TASQ-SC, respectively (see [Appendix 4](#)).

Each TASQ will be completed by the participant as outlined in the schedule of activities (see [Appendix 1](#)).

EORTC QLQ-C30

The QLQ-C30 is a validated, reliable self-report measure (Aaronson et al. 1993; Fitzsimmons et al. 1999) (see [Appendix 4](#)). It consists of 30 questions that assess five aspects of participant functioning (physical, emotional, role, cognitive, and social), three symptom scales (fatigue, nausea and vomiting, and pain), global health status and quality of life (QoL), and six single items (dyspnea, insomnia, appetite loss, constipation, diarrhea, and financial difficulties) with a recall period of the previous week. Scale scores can be obtained for the multi-item scales. The functioning and symptoms items are scored on a four-point scale that ranges from "not at all" to "very much", and the global health status and QoL items are scored on a seven-point scale that ranges from "very poor" to "excellent". The QLQ-C30 takes approximately 10 minutes to complete. The QLQ-C30 will be completed by the participant as outlined in the schedule of activities (see [Appendix 1](#)).

Healthcare Professional Questionnaires

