Appendix 1: Schedule of Activities

- q All women of childbearing potential will have a serum pregnancy test at screening, within 14 days prior to initiation of study treatment. Urine pregnancy tests (or serum, if urine is not feasible) will be performed at specified subsequent visits during treatment, at the treatment discontinuation visit, and may be required beyond treatment discontinuation, monthly for 5 months after the final dose of atezolizumab. Pregnancy tests after study treatment discontinuation can be performed at home. If a urine pregnancy test is positive, it must be confirmed by a serum pregnancy test.
- r In accordance with country-specific health authority mandates, pregnancy tests may be required beyond treatment discontinuation, monthly for 5 months after the final dose of atezolizumab. Pregnancy tests after study treatment discontinuation can be performed at home. If a home urine pregnancy test is positive, it must be confirmed by a serum pregnancy test and if confirmed, immediately communicated to the treating physician.
- s TSH, free T3 (or total T3 for sites where free T3 is not performed), and free T4 will be assessed on Day 1 of Cycle 1 and every four cycles thereafter (i.e., Cycles 5, 9, 13, etc.).
- t At screening, participants will be tested for HIV, HBsAg, HBsAb, total HBcAb, and HCV antibody. If a participant has negative HBsAg and HBsAb tests and a positive total HBcAb test at screening, an HBV DNA test must also be performed. If a participant has a positive HCV antibody test at screening, an HCV RNA test must also be performed.
- u Urinalysis includes pH, specific gravity, glucose, protein, ketones, and blood; dipstick permitted.
- v Urinalysis should be performed as clinically indicated during study treatment.
- w The Patient Preference Questionnaire (PPQ) must be completed following study treatment administration on Day 1 of Cycle 6 of the Treatment Cross-over Period. Participants who discontinued study treatment prior to study treatment Cycle 6 should complete the questionnaire at the time of discontinuation as long as they have received at least one dose of atezolizumab SC and atezolizumab IV post-randomization.

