- x Participants in Arm A will complete the Therapy Administration Satisfaction Questionnaire for SC administration (TASQ-SC) immediately following study treatment administration on Day 1 of Cycle 3 of the Treatment Cross-over Period and the Therapy Administration Satisfaction Questionnaire for IV administration (TASQ-IV) immediately following study treatment administration on Day 1 of Cycle 6 of the Treatment Cross-over Period. Participants in Arm B will complete the TASQ-IV and TASQ-SC immediately following study treatment administration on Day 1 of Cycle 3 and 6 of the Treatment Cross-over Period, respectively.
- y During the study treatment periods, participants must complete the EORTC QLQ-30 and EQ-5D-5L before the participant and clinician receives any information on disease status and prior to treatment administration on the scheduled visit day. EORTC QLQ-C30 and EQ-5D will be administered at Cycle 7, 10, 13, and 16 of the Treatment Continuation Period.
- z Each Healthcare Professional Questionnaire (HCPQ) will be completed by the applicable HCP after each study treatment preparation and/or administration for each participant. Applicable HCPs are described in each of the questionnaires (HCPQ-Treatment Room, HCPQ-Drug

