Appendix 4: Patient-Reported Outcome Measures

Study Number:	Subject Number:	Visit Name: Cycle  Day 
Site Number:	Date of Assessment:	

THERAPY ADMINISTRATION SATISFACTION QUESTIONNAIRE (TASQ-SC)*

Instructions: Cancer treatment can be given through an injection in your thigh.

Please answer the questions based on your most recent SC injection.

1. How satisfied or dissatisfied were you with the SC injection?

Very satisfied Satisfied Neither satisfied nor dissatisfied Dissatisfied Very dissatisfied

2. How much pain did you experience at the site of the SC injection?

None Mild Moderate Severe Very Severe

3. How much swelling did you experience at the site of the SC injection?

None Mild Moderate Severe Very Severe

4. How much redness did you experience at the site of the SC injection?

None Mild Moderate Severe Very Severe

5. When receiving the SC injection, how restricted did you feel?

Not at all A little bit Somewhat Quite a bit Very much

6. How convenient is it for you to get your SC injection?

Very convenient Convenient Neither convenient nor inconvenient Inconvenient Very inconvenient

7. How bothered are you by the amount of time it takes to have the SC injection?

Not at all bothered A little bothered Moderately bothered Quite bothered Very bothered

8. Does setting up the SC injection mean you lose or gain time for other things?

Lost a lot of time Lost some time Neither lost nor gained time Gained some time Gained a lot of time

Respondent Initials: _____ Date: _____

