However, if there are any missing responses within a domain then the domain will not be scored (i.e., a missing value is assigned to the domain).

Since the maximum possible item response value is 5 and the minimum possible response value is 1 for all TASQ items, a simpler way to represent the above formula for the TASQ domains is:

$$TASQ\ Domain\ Score = [\text{Mean of completed item responses} - 1] \times 25$$

Descriptive statistics will be computed for these three domains by randomized treatment sequence and overall.

The two domains that contain only one item (Psychological Impact and Impact on Activities of Daily Living) will be described by randomized treatment sequence and overall, in the same way as the patient satisfaction in Question 1: first as a categorical variable with the number and proportion of patient responses to each modality of the question, and secondly as a continuous variable with descriptive statistics.

The three descriptive questions (Q9, Q10, Q11) that are not part of the above domains will be summarized individually by the number and proportion of patient responses to each modality of the question.

The proportion of responses will be based on the number of patients who answered the respective question. All TASQ analyses will be performed on the FAS. The analysis will be done for all patients and as an exploratory analysis, as applicable, separately among participants with early-stage NSCLC and chemotherapy-naive participants with Stage IV NSCLC.

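### Each route's TASQ is given once, at that route's third planned dose, with no completion at an early stop, so early stoppers' satisfaction is lost for both SC and IV.

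*Protocol*

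**What the plan says.** **Timing.** In Protocol Appendix 1, Arm A completes the TASQ-SC "immediately following study treatment administration on Day 1 of Cycle 3 of the Treatment Cross-over Period" and the TASQ-IV after the Cycle 6 dose. For the other sequence, "Participants in Arm B will complete the TASQ-IV and TASQ-SC immediately following study treatment administration on Day 1 of Cycle 3 and 6". Routes change at Cycle 4, so each form falls at the third planned dose of its route. The end-of-treatment column is marked for the EORTC QLQ-C30 and EQ-5D-5L but not for the TASQ. Section 4.5.8.2 adds nothing: "Each TASQ will be completed by the participant as outlined in the schedule of activities".

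**Early stop.** Footnote w gives a rule for the PPQ only: "Participants who discontinued study treatment prior to study treatment Cycle 6 should complete the questionnaire at the time of discontinuation", provided they have had at least one dose of each route.

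**Stopping one route.** Section 4.3.2.1 states: "In case a participant develops unacceptable toxicity to the SC injection of atezolizumab, treatment with IV infusion may continue". The TASQ-SC form (Appendix 4) instructs: "Please answer the questions based on your most recent SC injection".

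**Analysis.** SAP Table 2 ties TASQ Question 1 to Cycle 3 or Cycle 6 according to arm. SAP 4.2.6 says: "The proportion of responses will be based on the number of patients who answered the respective question". SAP 4.1 mentions a sensitivity analysis for satisfaction on the full analysis set, but 4.2.6 does not define one.

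**The concern.** Satisfaction by route is the first-listed secondary objective. A rating taken only at the third dose leaves out people who stopped earlier, and some of them may have stopped because of their experience with the route. With a denominator of answerers, the reported percentage looks the same whether few or many are missing. The two questionnaires also differ without a stated reason. Someone in Arm B who stops after one SC injection at Cycle 4 is asked which route they preferred, but not how satisfied they were with that injection or how much pain, swelling or redness it caused.

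**Working it through.** **1. Who is lost, as written**

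| Course | TASQ-SC | TASQ-IV |
|---|---|---|
| Arm A, stops all treatment after Cycle 1 or 2 | lost | IV never received |
| Arm A, stops all treatment after Cycle 4 or 5 | obtained at Cycle 3 | lost |
| Arm B, stops all treatment after Cycle 1 or 2 | SC never received | lost |
| Arm B, stops all treatment after Cycle 4 or 5 | lost | obtained at Cycle 3 |
| Arm A, moved to IV before the Cycle 3 dose | due at Cycle 3, after an IV dose: ambiguous | due at Cycle 6 |
| Arm B, moved to IV before the Cycle 6 dose | due at Cycle 6, after an IV dose: ambiguous | obtained at Cycle 3 |

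In rows 2 and 4 the PPQ is collected at discontinuation and the TASQ is not.

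**2. Symmetry of all-cause stops.** Let N be randomized 1:1, with a fraction *a* stopping after dose 1 or 2 of the first route and a fraction *b* after dose 1 or 2 of the second. If stopping does not depend on route:

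- TASQ-SC lost = (N/2)a from Arm A + (N/2)b from Arm B
- TASQ-IV lost = (N/2)b from Arm A + (N/2)a from Arm B

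The totals are equal. A difference between routes needs route-dependent stopping.

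**3. The plan's own figure.** The sample size (Protocol 6.1, SAP 2.2) reproduces: 1.96² × 0.70 × 0.30 / 0.08² = 126.05, and 126 / (1 − 0.28) = 175. The 28% (0.28 × 175 = 49 people) is an allowance for missing preference answers. The documents give no TASQ missing rate, so below it serves only as an outer case.

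**4. What a responder-only percentage can conceal.** Let r be the satisfied proportion among answerers and m the share of exposed participants without a TASQ for that route. The rate among all exposed lies between r(1 − m) and r(1 − m) + m. With r = 80% (assumed):

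| m (assumed) | Lower | Upper |
|---|---|---|
| 5% | 76.0% | 81.0% |
| 10% | 72.0% | 82.0% |
| 20% | 64.0% | 84.0% |
| 28% | 57.6% | 85.6% |

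The reported figure is 80% in every row.

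**5. Direction for SC versus IV.** If the missing would be satisfied at rate s, the reported rate exceeds the all-exposed rate by m(r − s). The error in the SC − IV difference is therefore

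m_SC(r_SC − s_SC) − m_IV(r_IV − s_IV).

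Take r = 80% and s = 40% for both routes (assumed):

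- m_SC = m_IV = 5%: 2.0 − 2.0 = 0 points
- m_SC = 10%, m_IV = 5%: 4.0 − 2.0 = +2.0 points
- m_SC = 5%, m_IV = 10%: 2.0 − 4.0 = −2.0 points

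The sign depends on quantities that the documents do not give.

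**The case against.** A reader might infer that SC satisfaction is measured only in people who stayed on SC, and is therefore inflated relative to IV. The documents do not support this, for three reasons.

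- **Switchers are not excluded.** The TASQ is assigned by arm and cycle, and the form asks about the last SC injection. A participant moved to IV can still answer it.
- **The loss is not shown to be one-sided.** All-cause stops cost both routes. Section 4.3.2.1 keeps some SC-intolerant participants on study, where the TASQ-SC remains due. No move from IV to SC is described, and Appendix 9 lists permanent discontinuation for Grade 3 and 4 infusion-related reactions or cytokine release syndrome. Severely IV-intolerant participants may therefore be the ones who give no rating.
- **The size would be assumed.** With 90% of answerers satisfied, 3% to 10% missing and 20% to 50% of those satisfied, the all-exposed rate runs from 0.90 × 0.97 + 0.50 × 0.03 = 88.8% down to 0.90 × 0.90 + 0.20 × 0.10 = 83.0%, an overstatement of 1.2 to 7.0 points. None of these inputs comes from the documents. Protocol 1.6 reports that in Part 1 of the earlier SC study no Cycle 1 adverse event led to SC discontinuation, which suggests few stops for local intolerance.

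A sponsor could add that rating each route after three doses gives equal experience of both, that local reactions are also captured as adverse events in everyone dosed, and that SAP 4.2.2 keeps PPQ answers given before two consecutive doses of each route out of the primary analysis. These are good reasons to keep the third-dose answers as the main summary. They are not reasons to collect nothing at an early stop: the SAP's supplementary estimand already uses PPQ answers after one dose of each route.

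SAP 4.2.8 calls for PRO completion and reasons for missing data, but within the EORTC section and by time point and randomized arm. Even if read to cover the TASQ, it would not give completion among those exposed to each route.

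**Conclusion.** The gap is real but modest. Participants who stop all treatment after one or two doses of a route never rate that route, and the planned percentages do not show how many they are. For participants moved from SC to IV, the defect is an unclear instruction, not a stated exclusion. Both TASQ-SC and TASQ-IV are affected. Neither the direction nor the size of any bias in the SC versus IV comparison can be established. The ranges above rest on an assumed 80% satisfaction rate and assumed missing rates, and show only how wide the uncertainty could be. The endpoint is secondary and descriptive, the PPQ endpoint is untouched, and the sample size does not change. It is worth correcting because correction is cheap.

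**What to change.** **Protocol, footnote x.** Add that a participant who has had at least one dose of a route and stops it before its Cycle 3 or Cycle 6 dose completes that route's TASQ once, about the most recent dose of it. If treatment is discontinued, this is done at the discontinuation visit. If the participant moves to the other route, it is done at the visit of the move, before the first dose of the other route. This changes only when a questionnaire is given.

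**SAP 4.2.6.**
- Keep the third-dose answers as the main summary.
- Show early-stop answers in a separate row.
- Report TASQ completion against all who received at least one dose of that route.
- Define the satisfaction sensitivity analysis announced in SAP 4.1 as third-dose and early-stop answers combined.

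**Cost.** One footnote sentence, a few lines of SAP text, and an existing 12-item form at a visit that already takes place and, for discontinuers, already includes questionnaires. The downside is that a few answers will follow only one or two doses, with recall of up to about 30 days. That is why they belong in their own row.

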Appendix 1: Schedule of Activities

Preparation Area). Instructions for which questions should be completed in each questionnaire at each timepoint are indicated in the introduction to each questionnaire.

- ^{aa} Medication (e.g., prescription drugs, over-the-counter drugs, vaccines, herbal or homeopathic remedies, nutritional supplements) used by a participant in addition to protocol-mandated treatment from 7 days prior to initiation of study treatment until the treatment discontinuation visit.
- ^{bb} After informed consent has been obtained but prior to initiation of study treatment, only serious adverse events caused by a protocol-mandated intervention should be reported. After initiation of study treatment, all adverse events will be reported until 30 days after the final dose of study treatment or until initiation of new systemic anti-cancer therapy, whichever occurs first, and serious adverse events and adverse events of special interest will continue to be reported until 90 days after the final dose of study treatment or until initiation of new systemic anti-cancer therapy, whichever occurs first. After this period, all deaths, regardless of cause, should be reported. In addition, the Sponsor should be notified if the investigator becomes aware of any serious adverse event that is believed to be related to prior exposure to study treatment (see Section 5.6).
- ^{cc} Participants should receive their first dose of study drug on the day of randomization, if possible. If this is not possible, the first dose should occur no later than 5 days after enrollment. For administration instructions, please check the Pharmacy Manual.
- ^{dd} After Cycle 6, participants will select the route of administration (SC or IV) they would like to receive from Cycle 7 onwards.
- ^{ee} All measurable and evaluable lesions should be assessed and documented at screening. Tumor assessments performed as standard of care prior to obtaining informed consent and within 28 days prior to initiation of study treatment do not have to be repeated at screening, so long as they meet criteria outlined in Section 4.5.5. Screening assessments must include CT scans with contrast or MRI scans of the chest, abdomen, pelvis, and brain. A spiral CT scan of the chest may be obtained but is not a requirement. If a CT scan with contrast is contraindicated (e.g., in participants with impaired renal clearance), a non-contrast CT scan of the chest may be performed and MRI scans of the abdomen, pelvis, and brain should be performed. A CT scan with contrast or MRI scan of the brain must be done at screening to evaluate CNS metastasis in all participants (MRI scan must be performed if CT scan is contraindicated). An MRI scan of the brain is required to confirm or refute the diagnosis of CNS metastases at baseline in the event of an equivocal CT scan. Bone scans and CT scans of the neck should also be performed if clinically indicated. At the investigator's discretion, other methods of assessment of measurable disease as per RECIST v1.1 may be used.
- ^{ff} Participants will undergo tumor assessments as per local standard of care.

Appendix 2 Schedule of Pharmacokinetic and Immunogenicity Samples

Cycle	Day	Time/maximum window	PK sample	ADA sample
1	1	Predose	Atezolizumab (serum)	Atezolizumab (serum)
	4	Between 72 and 96 hours postdose	Atezolizumab (serum)	-
2–6, 8, and 16	1	Predose	Atezolizumab (serum)	Atezolizumab (serum)
Treatment discontinuation visit	At visit	At visit	Atezolizumab (serum)	Atezolizumab (serum)

ADA=anti-drug antibody; PK=pharmacokinetic.

Appendix 3

PK and ADA Sampling Instructions for Investigators

Body Sites for PK and ADA for Atezolizumab Sampling

In any case, precise blood drawing site must be recorded for all samples.

On days of SC dosing, PK/ADA blood samples should be drawn preferably from the arm. If a participant is unable to provide venous access from the arm, the hand or leg may be used as alternative back-up sites for PK blood sampling. If the leg is used to collect a PK blood sample, and atezolizumab SC was administered in the thigh, the opposite side from where atezolizumab has been most recently administered should be used. If atezolizumab was administered in the leg and the same leg where atezolizumab has been most recently administered must be used, the area of the injection should be avoided.

For IV dosing, PK/ADA blood samples need to be drawn from the arm not receiving atezolizumab infusion. If a participant is unable to provide venous access of the opposite arm from the infusion arm, the hand or leg may be used as alternative back-up sites for PK blood sampling.

Collecting blood for PK samples from central line and/or port should be avoided. If there is no possible way to avoid the central line and/or port, it is better to collect the PK sample than to avoid this altogether, but site of collection must be documented.

PK and ADA Sampling Time Variability Allowed

Every effort should be made to take PK and ADA samples on the exact day when they are scheduled (see [Appendix 2](#)) and prior to any infusion or injection is given (for predose samples). Our recommendation is to plan the first dose accordingly so that these key days fall into a day when the participant can attend the clinic.

In any case, exact actual sampling and dosing dates and times must be recorded for all samples.

